7.5 Efficacy evaluation

7.5.1 Children's Depression Rating Scale-Revised (CDRS-R)

At Visits 1 to 5, Visit 7, and Visit 8 or discontinuation of treatment, the severity of symptoms for the below 17 items will be judged using CDRS-R (Table 7-1). The date and results of evaluation will be recorded in the CRF. At discontinuation of treatment, evaluation will be performed if possible, and recorded in the CRF. The baseline is defined as Visit 2.

Table 7-1. Children's Depression Rating Scale-Revised

Endpoints	Score range	Endpoints	Score range
1. Impaired Schoolwork	1 to 7	11. Depressed Feelings	1 to 7
2. Difficulty Having Fun	1 to 7	12. Morbid Ideation	1 to 7
3. Social Withdrawal	1 to 7	13. Suicidal Ideation	1 to 7
4. Sleep Disturbance	1 to 5	14. Excessive Weeping	1 to 7
5. Appetite Disturbance	1 to 5	15. Depressed Facial Affect	1 to 7
6. Excessive Fatigue	1 to 7	16. Listless Speech	1 to 5
7. Physical Complaints	1 to 7	17. Hypoactivity	1 to 7
8. Irritability	1 to 7		
9. Excessive Guilt	1 to 7		
10. Low Self-Esteem	1 to 7		
		Total	17 to 113

7.5.2 Clinical Global Impression of Severity (CGI-S)

At Visits 1 to 8 or at discontinuation of treatment, the principal investigator or sub-investigator will evaluate the disease severity in terms of the below grades 1 to 7 (if the subject visits hospital for Visit 6, it will be performed if possible). The date and results of evaluation will be recorded in the CRF. At discontinuation of treatment, evaluation will be performed if possible, and recorded in the CRF. The baseline is defined as Visit 2.

- | | | | |
|------------------------|-------------------------|-----------------------------|---------------------|
| 1. Normal / no disease | 2. Bordering on disease | 3. Mild disease | 4. Moderate disease |
| 5. Marked disease | 6. Severe disease | 7. Extremely severe disease | |

7.6 Safety evaluation

7.6.1 Physical examination

At Visits 1 to 9, or discontinuation of the treatment or tapering period, and Visit 10, the principal investigator or sub-investigator will examine the subject by the standard methods in use at the relevant institution, and will ascertain the occurrence or non-occurrence of adverse events (if the subject visits hospital for Visit 6, it will be performed if possible). When an adverse event is found, the details will be recorded in the CRF. If necessary, examination appropriate to the signs and symptoms will also be performed, as judged appropriate by a physician. For 2 weeks after the initial administration of the study drug, the subject's progression will be monitored with special care.

7.6.2 Columbia Suicide Severity Rating Scale (C-SSRS)

At Visits 1 to 9, or at discontinuation of the treatment or tapering period, the principal investigator or sub-investigator will evaluate suicidal thinking using a questionnaire (if the subject visits hospital for Visit 6, it will be performed if possible). The date and results of evaluation will be recorded in the CRF. The principal investigator or sub-investigator will judge whether any abnormal change from baseline (Visit 2) is clinically significant (refer to Section 7.6.7.7) and will record any changes judged to be clinically significant as adverse events.

7.6.3 Body weight

Body weight (kg) will be measured at Visits 2 and 8, and Visit 9 (or at discontinuation of the treatment period or tapering period). The date and result of measurement will be recorded in the CRF. The principal investigator or sub-investigator will judge whether any abnormal change from baseline (Visit 2) is clinically significant (refer to Section 7.6.7.7) and will record any changes judged to be clinically significant as adverse events.

7.6.4 Blood pressure and pulse rate

The blood pressure (systolic and diastolic) and pulse rate, at rest, will be measured at Visits 1 to 9 (or at discontinuation of the treatment period or tapering period). If possible, this will be performed if the subject arrives at hospital for Visit 6. The date and results of measurement will be recorded in the CRF. The

principal investigator or sub-investigator will judge whether any abnormal change from baseline (Visit 2) is clinically significant (refer to Section 7.6.7.7), and will record any changes judged to be clinically significant as adverse events.

7.6.5 Electrocardiogram

Standard, 12-lead electrocardiogram (ECG) will be performed at Visits 1, 8 and 9 (or at discontinuation of the treatment period or tapering period). The principal investigator or sub-investigator will judge whether ECG results are normal or abnormal, and will record the date of ECG, the judgment, and any abnormal findings in the CRF. If there are abnormal findings, the principal investigator or sub-investigator will judge whether the abnormal change from baseline (Visit 1) is clinically significant (refer to Section 7.6.7.7), and will record any changes judged to be clinically significant as adverse events.

7.6.6 Laboratory tests

7.6.6.1 Laboratory test items

At Visits 1, 5, 8 and 9, or at discontinuation of the treatment period or tapering period, blood samples will be collected for laboratory tests, the volumes being 2 mL for hematology tests, and 8 and 5 mL for blood chemistry tests, at Visit 1 and other visits, respectively; and urine samples will also be collected. The samples will then be sent to the clinical laboratory facility specified in Section 7.6.6.2. Details of the collection, handling, storage, and shipment of samples are stipulated in a separate document.

The principal investigator or sub-investigator will judge whether any abnormal change from baseline (Visit 1) is clinically significant (see Section 7.6.7.7) and will record any changes judged to be clinically significant as adverse events. The sample collection dates will be recorded in the CRF for each sample type (blood or urine).

7.6.6.1.1 Routine tests

Table 7-2 shows the routine hematology test, blood chemistry test, and urinalysis parameters.

Table 7-2. Routine laboratory tests

Classification	Parameter
Hematology	Leukocyte count, erythrocyte count, hemoglobin, hematocrit, leukocyte fractions (eosinophils, basophils, neutrophils, monocytes, lymphocytes), platelet count
Blood chemistry	AST, ALT, LDH, γ -GTP, ALP, creatine kinase, total bilirubin, total protein, blood urea nitrogen, serum creatinine, uric acid, total cholesterol, triglycerides, Na, K, Cl, Ca, blood glucose, HbA1c ^a , TSH ^a , FT3 ^a , FT4 ^a
Urinalysis (qualitative)	Urinary protein, urinary glucose, urobilinogen, urinary occult blood

a: Only at Visit 1

[figure not shown]
7.6.6.1.2 Pregnancy test

At Visits 1 and 9, or at discontinuation of the treatment or tapering period, pregnancy will be determined

by the test for human chorionic gonadotropin in urine or serum (only with post-menarchic females).

7.6.6.2 Methods for collection, storage, and shipment of samples

An principal investigator, sub-investigator, nurse, or medical technician will collect blood and urine samples at the stipulated times, and send them to the below clinical laboratory facility. Details of the collection, handling, storage, and shipment of samples are specified in a separate document.

7.6.7 Evaluation of adverse events

7.6.7.1 Evaluation methods for adverse events

An adverse event is any unfavorable medical event suffered by someone administered a pharmaceutical product (including a study drug) and does not necessarily have a causal relationship with the relevant pharmaceutical product. In other words, an adverse event is any unfavorable and/or unexpected sign (including abnormal laboratory test result), symptom, or disease associated with the administration of a drug, irrespective of any causal relationship with that drug. Surgery that was already planned is not considered to be an adverse event, unless it leads to exacerbation of an existing disease, and is therefore not considered to be a serious adverse event even if it necessitates hospitalization. However, if an additional surgery is performed in connection with the planned surgery, this is taken to be an adverse event, and to be a serious adverse event if prolongation of hospitalization is required, or if any other criterion for being a serious adverse event is met. Hospitalization or prolongation of hospitalization for reasons other than adverse events is not considered to constitute a serious adverse event.

The presence or absence of an adverse event will be confirmed on the basis of the subject's spontaneous complaint, non-inductive questions, examination, C-SSRS, blood pressure, pulse rate, body weight, and ECG or laboratory test results. Adverse events include new onset of an event, increase in the severity or frequency of an event since administration initiation, and diagnostic abnormality, including abnormal laboratory test results. A symptom recorded as a medical history at study initiation will be handled as an adverse event only when symptoms are aggravated. In addition, loss of efficacy, and changes in the primary disease (depression) or scores for any of the CDRS-R items, will not be handled as adverse events in this study, unless judged to be serious adverse events.

The principal investigator or sub-investigator will evaluate adverse events. The principal investigator or sub-investigator will carefully investigate each adverse event, and record in the CRF the date of onset, time of onset, date of cessation (if the outcome is recovery or death), severity, seriousness (including the

reason for judging seriousness), causal relationship with the study drug, actions taken for the adverse event, and outcome of the adverse event.

7.6.7.2 Assessment period

Adverse events occurring between obtaining the legal representative's informed consent and 7 days after the final administration of study drug (the follow-up period) will be assessed. Adverse events that occur before initiation of administration in the extended long-term treatment study (study no.: 1702A3632), in subjects transferred to that study, will also be assessed. In the case of withdrawn subjects, the principal investigator or sub-investigator will assess adverse events up to 7 days after final administration of the study drug. Appropriate follow-up will be continued until one of the following, and the outcome will be determined on that basis: (i) the relevant adverse event recovers to the pre-administration state; (ii) the subject's condition stabilizes or becomes chronic; (iii) the subject is lost to follow-up; or (iv) the principal investigator or sub-investigator judges further assessment to be unnecessary. If the relevant subject transfers to the extended long-term treatment study (study no.: 1702A3632), follow-up of the adverse event will be continued after initiation of administration in that study, and it will be recorded in the CRF that the relevant adverse event continued after initiation of administration in the extended long-term treatment study. In addition, if the subject stops visiting hospital during the study, he/she will be followed up by an appropriate method such as by telephone, and the findings will be entered in the CRF.

If the above adverse event follow-up has to be continued for 28 days or more after completion of administration, the outcome at the earliest date after 28 days after completion of administration will be recorded in the CRF.

7.6.7.3 Severity

The principal investigator or sub-investigator will judge the severity of adverse events in accordance with the below definitions. The highest severity of each event during its period of occurrence will be recorded as the severity in the CRF.

- Mild: Signs or symptoms are found, but activities of daily life are not disturbed.
- Moderate: Activities of daily life are disturbed due to discomfort, and/or abnormality is clinically demonstrated.
- Severe: Activities of daily life are impossible, and/or major clinical effects are demonstrated.

7.6.7.4 Causal relationship with study drug

The principal investigator or sub-investigator will judge the causal relationship with the study drug in accordance with the following criteria:

- Not related: The adverse event can be clearly explained by a factor other than the study drug, and/or there is no valid chronological relationship between the study drug and the adverse event.

- Possibly related: The adverse event may have been caused by a factor other than the study drug, but a causal relationship with the study drug cannot be ruled out.
- Probably related: It is unlikely that the adverse event was caused by a factor other than the study drug.
- Related: There is a valid chronological relationship between administration of the study drug and onset of the adverse event, and the event cannot be explained by a factor other than the study drug

Adverse events judged to be “Possibly related”, “Probably related” or “Related” are taken to be adverse drug reactions.

7.6.7.5 Predictable adverse drug reactions

Adverse drug reactions listed in the most recent investigator’s brochure for duloxetine, or in any reports about adverse drug reactions submitted separately to the IRB, study site, or the principal investigator, are taken to be predictable adverse drug reactions.

7.6.7.6 Adverse events of special concern

7.6.7.6.1 Suicide-related adverse events

The duloxetine package insert, includes, as drug-class labeling, the following requirement to take great care: “There have been reports of increases in the risks of suicidal ideation and suicidal planning in patients aged under 24 administered antidepressants, so consideration should be given to the risk/benefit relationship when this drug is to be administered”. Therefore, the principal investigator or sub-investigator will evaluate any suicidal thinking using the C-SSRS questionnaire, as detailed in Section エラー! 参照元が見つかりません。 , and will record any suicide-related adverse events.

The principal investigator or sub-investigator will perform sufficient monitoring of subjects who suffer from adverse events that are clearly or possibly suicide-related.

If a subject suffers a suicide-related adverse event, and/or if requested by the sponsor, the principal investigator will report the details of the relevant adverse event to the sponsor, by fax, email or telephone, or orally. After the sponsor has received the relevant information, he/she will promptly request the Safety Evaluation Committee to perform a review. If necessary, the sponsor can also request the principal investigator to provide additional information.

7.6.7.7 Adverse events such as laboratory test results

The principal investigator or sub-investigator will judge whether or not any changes from the baseline by laboratory test results (hematology, blood chemistry, and urinalysis) and abnormalities in other safety endpoints (e.g. examination findings, body weight, blood pressure, pulse rate, ECG findings) are clinically significant. Laboratory test results that deviate from the reference range will be handled as abnormal values. If a baseline value is abnormal, but worsens after study initiation, the principal investigator or sub-

investigator will judge whether or not this is clinically significant. Events judged by the principal investigator or sub-investigator to be clinically significant will be recorded as adverse events. When an abnormal test result is accompanied by disease or other toxicity, the disease name and/or details of toxicity will be reported as an adverse event.

An event will be considered clinically significant if one or more of the following criteria is met, and judgment about clinical significance in other situations will be at the discretion of the principal investigator or sub-investigator:

- The criterion for a serious adverse event is met (refer to Section 7.6.7.8).
- Study drug discontinuation or dose reduction is required.
- Drug administration or another procedure is required for treatment.
- An additional test or other medical procedure is required.
- Management of abnormal hepatic function test results is necessary, and the discontinuation criteria (Appendix 2) are met.

If management of abnormal hepatic function test results is necessary, and the discontinuation criteria (Appendix 2) are met, evaluation and additional assessment will be performed, and records will be made in the follow-up assessment form for abnormal hepatic function.

7.6.7.8 Serious adverse events

7.6.7.8.1 Definition

Of the adverse events observed after study initiation, an adverse event meeting one or more of the following criteria will be handled as a serious adverse event:

- Leading to death.
- Life-threatening.
- Requiring hospitalization or prolongation of hospitalization.
- Leading to permanent and/or significant disability or dysfunction (according to the opinion of the reporting physician).
- Leading to congenital anomaly.
- Other medically major event.

If an adverse event exposes a subject to danger, or requires medical procedures to prevent one of the results defined above, even if the event does not lead to death, is not life-threatening, and does not require hospitalization, it will be handled as a serious adverse event on the basis of appropriate medical judgment. For example, bronchial asthma which requires intensive therapy at emergency department, etc., vascular disorder or convulsion not requiring hospitalization, drug dependency or abuse are included. In addition, all events meeting the below criterion are taken to be serious adverse events. The principal investigator or sub-investigator will judge the seriousness of adverse events.

- AST and/or ALT >3 times the upper limit of the respective reference values, and total bilirubin >2 times the upper limit of the reference values.

7.6.7.8.2 Reports of serious adverse events

The principal investigator will report the details of all serious adverse events to the sponsor, using the serious adverse event report form, within 24 hours after the relevant events are judged to be serious. All serious adverse events will be reported, irrespective of the causal relationship with the study drug. The sponsor can also request additional information about serious adverse events.

As far as possible, the principal investigator will report all serious adverse events using the diagnostic names. If the diagnostic name has not been fixed at the time of reporting, the report will state the individual signs and symptoms.

Serious adverse event reports and contact person for reporting
[REDACTED] [REDACTED] [REDACTED] [REDACTED] [REDACTED]
[REDACTED]
[REDACTED]
[REDACTED]
[REDACTED]

If the sponsor judges follow-up to be necessary, the principal investigator will report to the above contact person by fax or email, using a serious adverse event form, and will provide any new information to the sponsor. The principal investigator will evaluate photocopies of relevant documents, such as discharge summaries, medical records from other departments and institutions, and autopsy reports, and will include any relevant information in a supplementary serious adverse event report. The sponsor can also request photocopies of such reports.

The principal investigator will establish appropriate measures for medical treatment of serious adverse events, on the basis of medical judgment. Measures taken with serious adverse events, and their results, will be recorded. The principal investigator will establish the necessary measures, and will also elucidate the causes of serious adverse events as far as possible.

If a serious adverse event during or after the assessment period stipulated in Section 7.6.7.2 is judged by the principal investigator to have a causal relationship with study drug, he will report it to the sponsor.

The principal investigator will also report all serious adverse events to the IRB in accordance with the regulatory requirements. The sponsor will report all reported serious adverse events to the regulatory authority, in accordance with the regulatory requirements.

7.6.7.9 Abuse, misuse, overdose, and medication error (special situations)

In the event of abuse, misuse, overdose, or medication error associated with the study drug (special situations), as defined below, the principal investigator will promptly report it to the sponsor by fax or email, using the form stipulated by the sponsor (Special Situation Report Form). The principal investigator will also submit reports to the sponsor about any serious adverse events associated with the special

situation.

- Abuse: Intentional overdose of the study drug, associated with adverse physical or mental effects, irrespective of whether this is continuous or sporadic.
- Misuse: Inappropriate use of the study drug at doses other than those instructed or on the label, intentionally by the subject.
- Overdose: Accidental or intentional use of the study drug at a dose exceeding that prescribed.
- Medication error: An accidental medication error, including cases that have been prevented from occurring, during the process of prescription, dispensing or administration. A medication error due to the subject forgetting to take one or more doses is not reportable.

7.6.7.10 Pregnancy

The principal investigator or sub-investigator will instruct female subjects that, if they become pregnant during the study, they must stop taking the study drug, and immediately inform the principal investigator or sub-investigator. If a subject is found to be pregnant, the principal investigator or sub-investigator will withdraw her from the study. Information about the pregnancy will be reported to the sponsor as detailed below.

For all pregnancies that occur between initiation of study drug administration and completion of the follow-up period, the principal investigator will send a pregnancy follow-up report to the sponsor by fax or email within 24 hours after the pregnancy comes to light. Pregnancy complications and terminations for medical reasons will be reported appropriately, as adverse events or serious adverse events. Miscarriages will be reported as serious adverse events. In addition, pregnancies will be followed, and pregnancy follow-up reports will be submitted to the sponsor by fax or email. Even after completion of the follow-up period, if a pregnancy comes to light within 1 month after the final study drug administration, the study site will report it to the sponsor. At completion of pregnancy, by birth, miscarriage or termination, the outcome will be reported to the sponsor.

7.6.7.11 Adverse events during study drug administration

Adverse events with onset after the initial study drug administration are taken to be treatment-emergent adverse events.

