8.11 Safety analysis

8.11.1 Adverse events

Adverse events will be classified by system organ class and preferred term, in accordance with MedDRA. Of the adverse events reported using CRFs, treatment-emergent adverse events will be used for safety analysis. Treatment-emergent adverse events are defined in Section 7.6.7.11 .

The number of subjects suffering treatment-emergent adverse events, and the numbers suffering death, other serious treatment-emergent adverse events, treatment-emergent adverse events leading to discontinuation of administration, and treatment-emergent adverse events leading to dose reduction, will be determined for each treatment group. The treatment-emergent adverse event rate and 95% confidence interval will be calculated by the Clopper-Pearson method. The number of adverse events will also be included. Adverse drug reactions will be summarized in the same manner as treatment-emergent adverse events. Adverse drug reactions are defined in Section 7.6.7.4 .

As summarization of treatment-emergent adverse events by system organ class and preferred term, the number and proportion of subjects suffering these events will be shown for each treatment group. In addition, treatment-emergent adverse events will be summarized by severity, onset timing, and outcome. Adverse drug reactions will be summarized similarly.

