### 10.1 Adverse events and adverse drug reactions

Adverse events occurring at or after the initial administration of the study drug will be evaluated. Reported adverse events will be converted to Medical Dictionary for Regulatory Activities (MedDRA) terms, and tabulated by system organ class and preferred term.

- 1) For each treatment group, the number of subjects with a given adverse event and the number of cases will be determined, and the incidence rate and 95% confidence interval will be calculated. The incidence rate will be obtained as the proportion of subjects in the analysis set with a specific adverse event, and the confidence interval for the incidence rate will be determined by the Clopper-Pearson method. In addition, the incidence rates will be compared between treatment groups using Fisher's exact test. Totaling will be performed in a similar manner to above with deaths, other serious adverse events, adverse events leading to administration discontinuation, adverse events leading to dose reduction, adverse drug reactions, deaths as adverse drug reactions, other serious adverse drug reactions, adverse drug reactions leading to administration discontinuation, and adverse drug reactions leading to dose reduction. The relevant definitions are shown below.

Death	Adverse event with "Death" as the outcome
Other serious adverse event	Adverse event in the seriousness category "Serious", except for death
Adverse event leading to administration discontinuation	Adverse event for which the study drug action is "Administration discontinuation"
Adverse event leading to dose reduction	Adverse event for which the study drug action is "Dose reduction"
Adverse drug reaction	Adverse event with the causal relationship with the study drug judged to be other than "Not related"
Death as adverse drug reaction	Death, with the causal relationship with the study drug judged to be other than "Not related"
Other serious adverse drug reaction	Other serious adverse event with the causal relationship with the study drug judged to be other than "Not related"
Adverse drug reaction leading to administration discontinuation	Adverse event leading to administration discontinuation, with the causal relationship with the study drug judged to be other than "Not related"
Adverse drug reaction leading to dose reduction	Adverse event leading to dose reduction, with the causal relationship with the study drug judged to be other than "Not related"

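### Treatment-emergent events are defined by onset alone, so a symptom that starts before first dose and worsens on study drug can be missing from the adverse event tables

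*Protocol*

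**What the plan says.** Four sets of provisions bear on the point.

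- **Collection.** Under Protocol 7.6.7.2, events arising between the legal representative's "informed consent and 7 days after the final administration of study drug (the follow-up period) will be assessed". Screening is inside the window.
- **What counts as an adverse event.** Protocol 7.6.7.1: "Adverse events include new onset of an event, increase in the severity or frequency of an event since administration initiation". For pre-existing symptoms it adds: "A symptom recorded as a medical history at study initiation will be handled as an adverse event only when symptoms are aggravated".
- **How severity is stored.** Protocol 7.6.7.3: "The highest severity of each event during its period of occurrence will be recorded as the severity in the CRF".
- **Which events are analysed.** Protocol 7.6.7.11: "Adverse events with onset after the initial study drug administration are taken to be treatment-emergent adverse events". Protocol 8.11.1: "Of the adverse events reported using CRFs, treatment-emergent adverse events will be used for safety analysis". SAP 10.1: "Adverse events occurring at or after the initial administration of the study drug will be evaluated".

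**The concern.** The definition of an adverse event includes worsening after dosing starts. The filter that admits events to the analysis refers only to onset (Protocol) or occurrence (SAP) relative to first dose, and neither document connects the two. A symptom that first appears in screening and becomes worse on study drug can therefore fall between them.

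Worsening of a symptom already present is one way in which poor tolerability shows. If such cases are dropped, incidence is understated in both arms. If worsening is also more frequent on duloxetine, the between-arm difference shrinks. Adverse event occurrence and frequency are the stated indices of the secondary safety objective, so the selection rule should not depend on how a site happens to enter the record.

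**Working it through.** No figure in the plan is in dispute, so the check is mainly a comparison of provisions.

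**1. Can an event start before first dose?** Yes. Table 7-3 puts Visit 1 at day −21 to −7 and Visit 2 at day 0, and section 5.2 starts dosing the day after Visit 2. The interval from Visit 1 to first dose is thus 7 + 1 = 8 to 21 + 1 = 22 days, with event collection open throughout.

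**2. Does the medical-history rule cover it?** No. Section 7.2 takes as history important past illness, surgical history, and complications ongoing at informed consent. An event that begins after consent is outside that list, so the aggravation rule in 7.6.7.1 does not clearly reach it.

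**3. How is the worsening dated?** Two readings are open.

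| Reading | Basis | Record | Treatment-emergent? |
|---|---|---|---|
| New event | 7.6.7.1 counts the increase as an adverse event | Second record, dated at the worsening | Yes |
| Single record | 7.6.7.3 keeps one peak severity over the event's whole course | One record, onset in screening | No |

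No provision chooses between them. The CRF items listed in 7.6.7.1 are onset date and time, cessation date, severity, seriousness, causality, action taken and outcome. There is no date of worsening.

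**4. Does the SAP settle it?** No. Its selection sentence speaks of events occurring, which is looser than onset. But the date it uses to place an event is the onset date. The timing table computes onset date minus first-dose date plus 1, and the dose table uses the dose on the onset date. For nausea starting five days before first dose, the timing is −5 + 1 = −4, which precedes the first category (weeks 0 to 1).

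**5. Which outputs are exposed?**
- Exposed under the single-record reading: the adverse event and adverse drug reaction tables of 8.11.1 and SAP 10.1, including those for serious events, discontinuation and dose reduction, because SAP 10.1 totals these in the same way.
- Not exposed: vital signs and weight (SAP 10.2), laboratory results and liver thresholds (10.3), ECG shifts (10.4) and C-SSRS shifts (10.5). None depends on an event's onset date.

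**6. Scale.** The plan's arm size reproduces: 66 / (1 − 0.10) = 73.3, rounded up to 74. Assuming all 74 enter the safety set:
- one subject = 1/74 = 1.35 percentage points;
- two subjects = 2/74 = 2.70%.

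SAP 10.1 lists separately the preferred terms reaching 2% in at least one arm, and 0.02 × 74 = 1.48. Two subjects qualify and one does not, so a single omitted case can remove a term from that table.

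**The case against.** The strongest reply is that 7.6.7.1 and 7.6.7.11 can be read together without conflict. If an increase since dosing began is itself an adverse event, its natural onset is after first dose, and the filter admits it. Section 7.6.7.3 speaks of each event and does not say that a worsening belongs to the earlier one. CRF entry also follows separate procedures that are not in these documents. This reading is fair, and it means that omission is possible rather than certain. It does not close the gap, because nothing instructs sites to record the worsening that way and two sites could enter the same case differently.

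Two further replies stand and narrow the point.

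- Protocol 7.6.2 to 7.6.6 and 7.6.7.7 already turn clinically significant changes from baseline in C-SSRS, weight, vital signs, ECG and laboratory values into adverse events. Section 7.6.7.7 also names examination findings.
- Section 7.6.7.1 keeps changes in the depression itself or in CDRS-R item scores out of the adverse events unless serious. Sleep disturbance is item 4 and suicidal ideation item 13. Where that rule applies, non-serious worsening is excluded by it and not by the treatment-emergent definition. Item 13 and the somatic subscale, which includes item 4, are compared between arms as efficacy measures. Insomnia or suicidal thoughts are therefore poor examples of this gap.

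**Conclusion.** The gap is real but narrow. The treatment-emergent definition and SAP 10.1 are not reconciled with 7.6.7.1. Under the single-record reading, an event that begins between consent and first dose and worsens on study drug is absent from the adverse event and adverse drug reaction tables. It mainly affects symptom events, such as nausea or agitation, that are not captured through a measured safety variable or handled as a CDRS-R item change.

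Three stronger conclusions might be inferred, and the documents support none of them.

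- **That such events are lost from every by-arm safety table.** The C-SSRS, vital-sign, laboratory and ECG summaries do not use event onset.
- **That the definition contradicts 7.6.7.1.** That section defines adverse events, not treatment-emergent ones. The two are unreconciled, not opposed.
- **That a sizeable between-arm difference is hidden.** Assume 20% of 74 have an event ongoing at first dose, with worsening in 30% on duloxetine and 10% on placebo. That gives 74 × 0.20 × 0.30 = 4.44 against 74 × 0.20 × 0.10 = 1.48 subjects, or 4.0 points. With 5% ongoing and 10% worsening the loss is 74 × 0.05 × 0.10 = 0.37 subjects per arm. All these rates are assumed, and the calculation further assumes that no worsening is captured elsewhere. The documents give no rate, so neither size nor direction can be estimated beyond 1.35 points per omitted subject.

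**What to change.** - **Protocol 7.6.7.11 and SAP 10.1:** use one definition. An event is treatment-emergent if its onset is at or after first dose, or if it was present before first dose and then increases in severity, frequency or seriousness. This also removes the difference between the Protocol (after first dose) and the SAP (at or after first dose).
- **Protocol 7.6.7.3:** record such a worsening as a new event dated at the worsening, so that severity before and after first dose is kept. The definition alone is not enough, because pre-dose severity cannot be recovered from a record that holds only the peak.
- **Protocol 7.6.7.1:** leave the rule on CDRS-R item changes as it is.

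The SAP change belongs before the key break. The cost is two sentences and a CRF completion instruction, with slightly more events counted and no added visits or tests.
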